4.0 Study Calendars

4.1 Test Schedule (excluding routine investigations in the peri-ASCT period*)

Tests and procedures	Prior to Registration		Induction and consolidation ^{16,1}	Every cycle pre-treatment including maintenance ^{1,7}	End of Cycle 4 of induction, post ASCT between Day 60-120, end of consolidation and 1 year post initiation of maintenance ^{1,14}	End of Treatment (±14 days) ¹
	≤30 days	≤14 days				
Complete medical history	X				X	
Adverse Event monitoring		X		X	X	X
Physical exam, including weight and vital signs		X		X	X	X
Height		X			X	
Performance status (ECOG scale)		X		X	X	X
Serum pregnancy test		X ¹¹				
CBC with differential		X	X ¹⁵	X ¹⁵	X	X
Chemistry group: sodium, potassium, glucose, alkaline phosphatase; total and direct bilirubin; SGOT (AST); SGPT (ALT), serum creatinine, calcium		X		X	X	X
HIV, hepatitis B and C	X					
LDH, Beta ₂ -microglobulin, C-reactive protein	X				X	
Electrophoresis of serum and urine (SPEP/UPEP)		X		X ³	X	X ³
Affected immunoglobulin ²		X		X ²	X	X ²
Immunofixation serum and urine	X			X ⁴	X	X ⁴
Immunoglobulin free light chain (MML panel)		X		X ⁵	X	X ⁵
ECG	X					
X-ray skeletal survey or whole-body low-dose CT	X			X ⁶	X ⁶	X
CT Scan, PET/CT, or MRI for measurement if evidence of prior EMD lesion ⁸	X			X ⁸	X ⁸	
Circulating plasma cell assessment (flow cytometry or peripheral smear) ⁹		X		X ⁹	X ⁹	
Bone marrow aspirate and biopsy for myeloma ¹⁷	X			X ¹⁰	X ¹⁰	X

Tests and procedures	Prior to Registration		Induction and consolidation ^{16,1}	Every cycle pre-treatment including maintenance ^{1,7}	End of Cycle 4 of induction, post ASCT between Day 60-120, end of consolidation and 1 year post initiation of maintenance ^{1,14}	End of Treatment (± 14 days) ¹
	≤ 30 days	≤ 14 days				
Chest x-ray	X					
Register patient for POMALYST REMS TM program		X ¹²				
Patient Medication Diary (Appendix II) ¹³				X	X	X
Mandatory Research Bone marrow sample ¹⁸	X ¹⁴				X ¹⁴	

*Performed per institutional guidelines. Melphalan conditioning followed by stem cell infusion is being considered as ‘cycle 5’ in the protocol for logistical reasons only. No additional toxicity data will be collected in the immediate post ASCT period until day 60-100 when the patient returns for routine post-ASCT reevaluation.

- 1) All scheduled visits are while patient is receiving therapy will have a window of ± 7 days unless otherwise stated.

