7.0 Protocol Treatment

7.1 Cycle lengths:

Cycles 1-3 = 28 days
 Cycle 4 = up to 56 days
 Cycle 5 = up to 120 days
 Cycles 6-8 = 28 days
 Cycle 9 = up to 56 days
 Cycles 10 and beyond = 28 days

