7.2 Treatment Schedule

	Doses and Schedule				
	Agent	Dose Level	Route	Day	Retreatment
Cycles 1-4 Induction (x 4 cycles)	Ixazomib	4 mg	PO	1, 8, 15	Every 28 days
	Pomalidomide	4 mg	PO	Days 1-21	Every 28 days
	Dexamethasone	40 mg	PO	1, 8, 15, 22	Every 28 days
Cycle 5 Transplantation ^{a,e,f}	Stem cell mobilization ^b followed by single ASCT				
Cycles 6-9 Consolidation ^c (x 4 cycles)	Ixazomib	4 mg	PO	1, 8, 15	Every 28 days
	Pomalidomide	2 mg	PO	Days 1-21	Every 28 days
	Dexamethasone	40 mg	PO	1, 8, 15, 22	Every 28 days
Cycles 10 and Beyond Maintenance (until progression or unacceptable toxicity) ^d	Ixazomib	4 mg	PO	1, 8, 15	Every 28 days

- SCT:** Can be performed per institutional practice. Stem cells collected and cryopreserved ahead of time or collected immediately prior to transplant can be used. Conditioning regimen preference left to the treating physician, but should not be enrolled in any additional therapy trials.
- If not previously collected and cryopreserved.
- If a patient previously has a dose reduction in induction, the consolidation phase will start and continue at reduced dose.
- Ixazomib maintenance would start at 4 mg unless dose has been previously reduced in the Induction or consolidation phase due to a non-hematologic toxicity specifically attributed to Ixazomib.
- Window period is 2-4 weeks between Induction and ASCT; 60-120 days between ASCT and Consolidation and 0-4 weeks between the Consolidation and Maintenance phases.
- Melphalan conditioning followed by stem cell infusion is being considered as 'cycle 5' for logistical reasons only. No additional toxicity data will be collected in the immediate post ASCT period until day 60-100 when the patient returns for routine post ASCT-reevaluation.

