10.62 All other AEs

Submit via appropriate MCCC Case Report Forms (i.e., paper or electronic, as applicable) the following AEs experienced by a patient and not specified in Section 10.6:

10.621 Grade 2 AEs deemed *possibly, probably, or definitely* related to the study treatment or procedure.

10.622 Grade 3 and 4 AEs regardless of attribution to the study treatment or procedure.

10.623 Grade 5 AEs (Deaths)

10.6231 Any death within 30 days of the patient's last study treatment or procedure regardless of attribution to the study treatment or procedure.

10.6232 Any death more than 30 days after the patient's last study treatment or procedure that is felt to be at least possibly treatment related must also be submitted as a Grade 5 AE, with a CTCAE type and attribution assigned.

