10.8 Additional instructions Special reporting requirements for Millennium

AEs may be spontaneously reported by the patient and/or in response to an open question from study personnel or revealed by observation, physical examination, or other diagnostic procedures. Any clinically relevant deterioration in laboratory assessments or other clinical finding is considered an AE. When possible, signs and symptoms indicating a common underlying pathology should be noted as one comprehensive event. For serious AEs, the investigator must determine both the intensity of the event and the relationship of the event to study drug administration.

AEs which are serious must be reported to Millennium Pharmacovigilance (or designee) from the first dose of study drug through 30 days after administration of the last dose of ixazomib. Any SAE that occurs at any time after completion of ixazomib treatment or after the designated follow-up period that the sponsor-investigator and/or sub-investigator considers to be related to any study drug must be reported to Millennium Pharmacovigilance (or designee). In addition, new primary malignancies that occur during the follow-up periods must be reported, regardless of causality to study regimen, for a minimum of three years after the last dose of the investigational product, starting from the first dose of study drug. All new cases of primary malignancy must be reported to Millennium Pharmacovigilance (or designee).

Planned hospital admissions or surgical procedures for an illness or disease that existed before the patient was enrolled in the trial are not to be considered AEs unless the condition deteriorated in an unexpected manner during the trial (e.g., surgery was performed earlier or later than planned). All SAEs should be monitored until they are resolved or are clearly determined to be due to a patient's stable or chronic condition or intercurrent illness(es).

Since this is an investigator-initiated study, the principal investigator, [name], also referred to as the sponsor-investigator, is responsible for reporting serious adverse events (SAEs) to any regulatory agency and to the sponsor- investigator's EC or IRB.

Regardless of expectedness or causality, all SAEs (including serious pretreatment events) must also be reported in English to Millennium Pharmacovigilance (or designee):

Fatal and Life Threatening SAEs within 24 hours of the sponsor-investigator's observation or awareness of the event

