16.42 Adverse Event Stopping Rules

The stopping rules specified below are based on the knowledge available at study development. We note that the Adverse Event Stopping Rule may be adjusted in the event of either (1) the study re-opening to accrual or (2) at any time during the conduct of the trial and in consideration of newly acquired information regarding the adverse event profile of the treatment(s) under investigation. The study team may choose to suspend accrual because of unexpected adverse event profiles that have not crossed the specified rule below.

Accrual will be temporarily suspended to this study if at any time we observe events considered at least possibly related to study treatment (i.e. an adverse event with attribute specified as “possible,” “probable,” or “definite”) that satisfy one of the following:

- if 3 or more patients in the first 10 treated patients experience a grade 4 or higher non-hematologic adverse event at least possibly related to treatment.
- if after the first 10 patients have been treated, 30% of all patients experience a grade 4 or higher non-hematologic adverse event at least possibly related to treatment.

We note that we will review grade 4 and 5 adverse events deemed “unrelated” or “unlikely to be related”, to verify their attribution and to monitor the emergence of a previously unrecognized treatment-related adverse event.

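### The cycle 5 footnote stops toxicity collection after ASCT until day 60-100, but Section 10 has no transplant exception and Section 16 does not say which rule the AE analysis follows

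*Combined protocol and SAP*

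**What the plan says.** **The exclusion.** The Section 7.2 footnote on cycle 5 states: "No additional toxicity data will be collected in the immediate post ASCT period until day 60-100". The same instruction appears in the notes to the schema ahead of Section 1.0 and under the Section 4.1 test schedule, whose title adds "excluding routine investigations in the peri-ASCT period". The sentence just before it says that conditioning and infusion are called cycle 5 only for logistical reasons. Section 7.1 gives the length: "Cycle 5 = up to 120 days".

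**The reporting rules.** Section 10.622 requires "Grade 3 and 4 AEs regardless of attribution to the study treatment or procedure". Section 10.4 requires any SAE, related or not. Section 10.8 sends SAEs to the drug supplier "from the first dose of study drug through 30 days after administration of the last dose of ixazomib". Section 10.1 adds that events reported by the expedited route must also enter the routine data. The exceptions in Section 10.32 are by event term and grade, and lapse on hospitalization; none concerns the transplant period.

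**The analysis.** The adverse-event paragraph of Section 16.32 takes each patient's maximum grade for each event type and excludes no phase. Section 16.42 suspends accrual "if at any time we observe events considered at least possibly related to study treatment", at 3 or more of the first 10 treated patients, or 30% of all patients after that, counting grade 4 or higher non-hematologic events.

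**The concern.** A site holding both instructions has no way to tell which applies to a grade 3 infection three weeks after stem cell infusion. Different sites, or different coordinators, could resolve it differently.

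Goal 2.1 describes a regimen of induction, ASCT, consolidation and maintenance. Sections 1.2 and 1.6 say that the impact of induction before salvage ASCT has not been studied systematically. A toxicity table for that regimen that leaves out the weeks after transplant, without saying so, would be read as covering all of it. The same data feed the twice-yearly DSMB review (16.41) and any decision to terminate (16.25).

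**Working it through.** **1. Footnote against Section 10**

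| Event after ASCT, before day 60-100 | Footnote | Section 10 |
|---|---|---|
| Grade 3-4, not serious, term outside the 10.61 list | not collected | submitted (10.622) |
| Term on the 10.61 list (such as sepsis) | not collected | graded at each evaluation; no statement that the post-ASCT visit looks back to conditioning |
| SAE, patient later resumes ixazomib | not mentioned | reported (10.4, 10.8) |
| SAE, patient never resumes | not mentioned | depends on the 30-day window (step 2) |
| Death | not mentioned | reported under 10.52; also seen through PFS18 and OS |

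The first row is a direct conflict. The others are unsettled.

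**2. SAE window for a patient who never resumes ixazomib.** The last induction dose is cycle 4 day 15. With a 28-day cycle 4 and the 2-4 week window before ASCT (7.2), transplant falls (28 - 15) + 14 = 27 to (28 - 15) + 28 = 41 days after that dose. A 30-day window therefore closes between 3 days after and 11 days before transplant. After it closes, only SAEs at least possibly related must be reported. For a patient who resumes, the window contains the whole interval.

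**3. Length of the gap.** Study entry to maintenance, from the 7.2 cycles and windows without dosing delays:
- shortest: 112 + 14 + 60 + 112 + 0 = 298 days
- longest: 112 + 28 + 120 + 112 + 28 = 400 days

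The gap is 60 to 100 days of this, or 60/120 = 50% to 100/120 = 83% of the maximum cycle 5.

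**4. Stopping rule, illustration only.** The plan states no operating characteristics for the 16.42 rule, so there is no figure to reproduce. Let q1 be a patient's risk of a qualifying event outside the gap and q2 the risk inside it. Both are assumptions; the documents give neither. Then q = 1 - (1 - q1)(1 - q2), and P(at least 3 of 10) = 1 - Σ(k=0..2) C(10,k) q^k (1 - q)^(10-k). For q = 0.10 this is 1 - (0.3487 + 0.3874 + 0.1937) = 0.070.

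| q1 | gap events never counted | q2 = 0.05 | q2 = 0.10 | q2 = 0.20 |
|---|---|---|---|---|
| 0.05 | 0.012 | 0.066 | 0.167 | 0.444 |
| 0.10 | 0.070 | 0.167 | 0.292 | 0.562 |
| 0.15 | 0.180 | 0.300 | 0.429 | 0.669 |

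The contrast with the second column is an upper bound. It assumes that every gap event is attributed to study treatment and that none arrives as an SAE. If all qualifying events arrive as SAEs, or if ASCT is not study treatment, the loss is zero. At q1 = 0.10 and q2 = 0.20 the loss thus lies anywhere from 0 to 0.562 - 0.070 = 0.492.

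**5. Timing.** At 2 patients per month (16.23) the tenth enrols at about month 5 and the twenty-fifth at 12.5. ASCT falls 126 to 140 days after entry, so the day 60-100 visit falls at 186 to 240 days, or 6.1 to 7.9 months. For the tenth patient that is about month 11 to 13. Section 16.23 also gives an enrolment period of about 2 years, which would leave more accrual to protect.

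**The case against.** The exclusion is deliberate. It is written three times, ASCT follows institutional practice, conditioning is left to the physician, and Section 1.2 reports an expert panel that regards salvage ASCT as standard in this setting. Not collecting the familiar toxicity of a standard procedure is a defensible choice. That stands as an explanation of intent, but neither Section 10 nor Section 16 carries it through.

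The footnote may also mean routine AE forms only. Expedited reporting is a separate stream that it does not mention, a life-threatening event is serious by definition under 10.4, and 10.1 carries expedited events into the routine data. AE monitoring is marked at the post-ASCT visit in Section 4.1, and nothing bars recording earlier events there. This stands, and it limits the point.

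A reader might go further in four ways that the documents do not support:
- **That the stopping rule is blind after transplant.** If Section 10 governs, SAEs and deaths still arrive.
- **That 16.42 contradicts the footnote.** Its wording on timing concerns events that have been observed; it does not mandate collection.
- **That this is the riskiest phase of the regimen.** No transplant-phase AE rates are given.
- **That delayed count recovery would be lost.** It is hematologic, so the rule would not count it, and engraftment times are collected and analysed under 16.33.

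**Conclusion.** The conflict between the cycle 5 footnote and Section 10 is real and needs a written resolution. What is firmly at risk is the completeness of the AE table and DSMB reports for non-serious post-transplant events over 60 to 100 days. Serious events are at risk only if the footnote is taken to override 10.4 and 10.8, or if a patient never resumes ixazomib and the 30-day window has closed. Separately, 16.42 does not say whether ASCT is study treatment, so collection alone would not settle what the rule counts.

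No size can be put on the stopping-rule effect. The step 4 figures rest on assumed rates and on the extreme case for attribution and reporting, and on the stated accrual rate much of the information would come late for a rule that only suspends accrual. The efficacy design is untouched.

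**What to change.** 1. State that SAE reporting under 10.4 and 10.8 continues through the transplant period on its usual timelines, including for patients who do not resume ixazomib.
2. At the existing post-ASCT visit, record from the medical record the grade 3-5 non-hematologic AEs since conditioning, with attribution, including the 10.61 terms.
3. Either limit the footnote to lower-grade and expected hematologic events, in all three places, or add a matching exception to 10.62. Align its day 60-100 with the day 60-120 visit column in 4.1.
4. Tabulate the ASCT phase separately in the AE analysis and DSMB reports.
5. State in 16.42 whether ASCT-phase events count, and hence whether ASCT is study treatment for that rule.

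The cost is modest extra data entry at a visit where AE monitoring is already scheduled, for about 25 patients. Treatment, sample size and the primary endpoint do not change.

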7.3 Dosing of ixazomib

The doses of ixazomib used in this study are based on data from Takeda's ongoing phase I and II trials, specifically the phase I/II trial of ixazomib (C16005) in combination with lenalidomide and dexamethasone, estimated 4 mg weekly of ixazomib as the RP2D in combination with weekly full dose of lenalidomide (25 mg) and dexamethasone (40 mg).

7.4 How to take ixazomib

Patients should be instructed to swallow ixazomib capsules whole, with water, and not to break, chew, or open the capsules. The ixazomib should be taken on an empty stomach (no food or drink apart from 240 mL of water), at least 1 hour before or no sooner than 2 hours after food. Each capsule should be swallowed separately with a sip of water. A total of approximately 240 mL (about 1 cup/8 oz) of water should be taken with the capsules.

Missed doses can be taken as soon as the patient remembers as long as the next scheduled dose is 72 hours or more away. Patients who vomit a dose after ingestion will not receive an additional dose, but should resume dosing at the time of the next scheduled dose.

Drug will be administered only to eligible patients under the supervision of the investigator or identified sub-investigator(s). The drug will be prepared under the supervision of a pharmacist, or appropriately qualified and trained personnel.

7.5 Pomalidomide supply - POMALYST REMS™ program

All patients will be registered to the Celgene POMALYST REMS™ program to obtain pomalidomide, as required by the US Food and Drug Administration (FDA). Patients will receive pomalidomide every 28 days. All unused study drug must be returned to Mayo Clinic to be recorded. Study drug is to be handed back to the patient to return per POMALYST REMS™ policy. **Only enough pomalidomide for one cycle of therapy will be supplied to the patient each cycle.** See [Appendix IV](#) for pomalidomide information.

7.6 Treatment at enrolling institution

For this protocol, the patient must return to the consenting institution for evaluation at least every 28 days. Treatment by a local medical doctor (LMD) is not allowed.

8.0 Dosage Modification Based on Adverse Events

Strictly follow the modifications in this table for the first **two** cycles, until individual treatment tolerance can be ascertained. Individual drugs can be dose reduced as per the table below depending on the adverse event attribution. Thereafter, these modifications should be regarded as guidelines to produce mild-to-moderate, but not debilitating, side effects. If multiple adverse events are seen, administer dose based on greatest reduction required for any single adverse event observed. Reductions apply to treatment given in the preceding cycle and are based on adverse events observed since the prior dose.

NOTE: If either of pomalidomide or ixazomib is discontinued, the patient can continue on the other drugs, unless specified otherwise in the dose modification tables. If both are discontinued, the patient will go to event monitoring (Section 18.0).

ALERT: *ADR reporting may be required for some adverse events (See Section 10)8.1*

Dose Levels for each drug in the combination

(Based on Adverse Events in Tables 8.2-4)

NOTE: One drug can be reduced each time based on the drug most likely related to the toxicity observed.

Ixazomib (Days 1, 8, 15)		Pomalidomide (Day 1-21)		Dexamethasone (Days 1, 8, 15, 22)	
Starting dose	4 mg	Starting dose	4 mg	Starting dose	40 mg
-1	3 mg	-1	3 mg	-1	20 mg
-2	2.3 mg	-2	2 mg	-2	12 mg
-3	2.3 mg Days 1, 15	-3	1 mg	-3	4 mg
-4	Discontinue	-4	Discontinue	-4	Discontinue

If patients cannot tolerate dose level –3 of ixazomib AND pomalidomide they will go to event monitoring per Section 4.2. If dexamethasone is discontinued, the patient may continue treatment.

8.11 Instruction for initiation of a new cycle of therapy

A new cycle of treatment may begin on the scheduled Day 1 of a new cycle if:

- The ANC is $\geq 1.0 \times 10^9/L$ (=1000/microliter)
- The platelet count is $\geq 75 \times 10^9/L$ unless the participant has $\geq 50\%$ bone marrow infiltration in which case a platelet count of $\geq 50 \times 10^9/L$ is allowed
- Any other non-hematologic treatment -related adverse event that may have occurred has resolved to \leq Grade 1 or baseline severity.

If these conditions are not met on Day 1 of a new cycle, the subject will be evaluated weekly and a new cycle of therapy will be held until the toxicity has resolved as described below

If any drug dosing was halted during the previous cycle and was restarted with a one-level dose reduction without requiring an interruption for the remainder of the cycle, then that reduced dose level will be initiated on Day 1 of the new cycle.

If any drug dosing was omitted for the remainder of the previous cycle or if the new cycle is held due to known hematologic toxicity newly encountered on the scheduled Day 1, then the new cycle will be started with a one-level dose reduction. If a new cycle of therapy cannot be restarted within 4 weeks of the scheduled Day 1 due to non-resolution of drug related toxicities, the patient will be removed from protocol therapy and will go to event monitoring.

→ → Use the NCI Common Terminology Criteria for Adverse Events (CTCAE) version 4.0* unless otherwise specified ← ←

8.2 Dose modifications for ixazomib based on adverse events during a cycle (for each cycle during induction and consolidation and maintenance)

CTCAE System/Organ/Class (SOC)	ADVERSE EVENT	AGENT[#]	ACTION^{**}
Blood and lymphatic system disorders	Febrile neutropenia If platelet count $<30 \times 10^9/L$ or ANC $<1.0 \times 10^9/L$ or ANC $>1.0 \times 10^9/L$ (up to LLN) with fever (temperature $>38.5^\circ C$)	Ixazomib	Days 2-15: Ixazomib dose should be omitted. Complete blood count (CBC) with differential should be followed weekly. If ANC is $\geq 1.0 \times 10^9/L$ and/or platelet counts $\geq 30 \times 10^9/L$, ixazomib may be reinitiated with 1 dose level reduction (see Table 8.1). The subsequent cycle will use the reduced dose
Nervous System Disorders	Peripheral motor neuropathy OR Peripheral sensory neuropathy Newly developed Grade 1 with pain or \geq Grade 2	Ixazomib	Reduce dose of ixazomib to the next lower dose level
	Grade 2 with pain or Grade 3	Ixazomib	Omit ixazomib until AE resolves or returns to baseline. When AE resolves, re-initiate ixazomib at the next lower dose level.
	Grade 4	Ixazomib	Omit ixazomib. Peripheral neuropathy should be monitored until toxicity resolves or returns to baseline. Upon recovery, if the patient has received clinical benefit from therapy with ixazomib, the investigator may consider restarting ixazomib at the next lower dose level
Skin and subcutaneous tissue disorders	Rash, maculo-papular Rash, acneiform Grade 2 or 3	Ixazomib	Omit ixazomib until rash resolves to \leq Grade 1 (See Section 9.9a). Restart at same dose. If the rash recurs, reduce dose by one dose level.
	Grade 4		Discontinue ixazomib

CTCAE System/Organ/Class (SOC)	ADVERSE EVENT	AGENT[#]	ACTION^{**}
Other	Any other non-hematological Grade 3 attributable adverse event except:	Ixazomib Pomalidomide Dexamethasone	Omit ixazomib or pomalidomide or both depending on the attribution to either or both drugs, until resolution to Grade ≤1 or baseline. Restart at next lower dose - If a patient is already at the lowest drug level, go to event monitoring. If the toxicity can be attributed to either of the drugs, pomalidomide should be discontinued at first instance followed by ixazomib for recurrence of the same toxicity necessitating dose modification.
Gastrointestinal Disorders	Grade 3 nausea and/or emesis in the absence of optimal anti-emetic prophylaxis Grade 3 diarrhea that occurs in the absence of optimal supportive therapy		
General disorders and administration site conditions	Grade 3 fatigue (consider relatedness to one or all of the components of the combination)		
Other	Grade 4 Nonhematologic adverse events (consider relatedness to one or all of the components of the combination)	Ixazomib Pomalidomide Dexamethasone	Consider permanently discontinuing ixazomib or pomalidomide or dexamethasone or all three depending on the attribution to either one, two or all three drugs (exception would be if the investigator determines the patient is obtaining a clinical benefit) If both ixazomib and pomalidomide are discontinued, the patient will go to event monitoring.

* Located at http://ctep.cancer.gov/protocolDevelopment/electronic_applications.ctc.htm

** Use the following to describe actions in the Action column:

- Omit = The current dose(s) for the specified drug(s) during a cycle is skipped. The patient does not make up the omitted dose(s) at a later time
- Hold/Delay = The current dose(s) of all drugs during a cycle is delayed. The patient does make up the delayed dose(s) when the patient meets the protocol criteria to restart drugs.
- Discontinue = The specified drug(s) are totally stopped.

NOTE: For adverse events attributable to both ixazomib and pomalidomide, only one of the drugs should be reduced for each incidence of AEs severe enough to necessitate dose reduction. The drug reduced should alternate starting with pomalidomide for the first dose reduction.

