8.3 Dose modifications for pomalidomide based on adverse events during a cycle

(For each cycle during induction and consolidation and maintenance)

Table 8.3			
CTCAE System/Organ/Class (SOC)	ADVERSE EVENT	AGENT	ACTION**
Investigations	Neutrophil count decreased If ANC $<1.0 \times 10^9/L$ or ANC $>1.0 \times 10^9/L$ (up to LLN) with fever (temperature $>38.5^\circ C$)	Pomalidomide	Omit pomalidomide dose. Follow CBC weekly. If neutropenia has resolved to \leq Grade 2 prior to Day 21 and fever has resolved, restart pomalidomide at next lower dose level and continue through Day 21 of a 28-day cycle. If febrile neutropenia is the only toxicity for which a dose reduction is required, G-CSF may be used and the pomalidomide dose maintained.
Investigations	Platelet count decreased If platelet count $<30 \times 10^9/L$	Pomalidomide	Omit pomalidomide dose Follow CBC weekly Hold anticoagulation/antiplatelet therapy until platelets $\geq 50,000/mm^3$ If platelet count resolves to \leq Grade 2 prior to Day 21, restart pomalidomide at next lower dose level and continue through Day 21 of each cycle
Skin and subcutaneous tissue disorders	Rash maculopapular Grade 2 or 3	Pomalidomide	Omit pomalidomide dose; follow weekly If the AE resolves to \leq Grade 1 prior to Day 21, restart pomalidomide at next lower dose level and continue through Day 21 of each cycle
	Grade 3-4 Stevens –Johnson Syndrome	Pomalidomide	Discontinue pomalidomide and remove patient from all study treatment
	\geq Grade 3 Erythema multiforme	Pomalidomide	Discontinue pomalidomide and remove patient from all study treatment

Table 8.3			
CTCAE System/Organ/Class (SOC)	ADVERSE EVENT	AGENT	ACTION**
	Erythroderma ≤Grade 3	Pomalidomide	Omit pomalidomide dose; follow weekly If the AE resolves to ≤Grade 1 prior to Day 21, restart pomalidomide at next lower dose level and continue through Day 21 of the 28-day cycle
	Rash, maculo-papular Rash, acneiform Grade 4	Pomalidomide	Discontinue pomalidomide and remove patient from all study treatment
Nervous system disorders	Peripheral sensory neuropathy Grade 3	Pomalidomide	Omit pomalidomide dose and follow at least weekly. If the AE resolves to ≤Grade 1 prior to Day 21, restart pomalidomide at next lower dose level and continue through Day 21 of the 28-day cycle
	Peripheral sensory neuropathy Grade 4	Pomalidomide	Discontinue pomalidomide and remove patient from all study treatment

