In line with clinical practice, dermatology consult and biopsy of Grade 3 or higher rash or any SAE involving rash is recommended. Prophylactic measures should also be considered if a patient has previously developed a rash (e.g., using a thick, alcohol-free emollient cream on dry areas of the body or oral or topical antihistamines). A rare risk is Stevens-Johnson Syndrome, a severe and potentially life-threatening rash with skin peeling and mouth sores, which should be managed symptomatically according to standard medical practice. Punch biopsies for histopathological analysis are encouraged at the discretion of the investigator.

9.9b Thrombocytopenia

Blood counts should be monitored regularly as outlined in the protocol with additional testing obtained according to standard clinical practice. Thrombocytopenia may be severe but has been manageable with platelet transfusions according to standard clinical practice. Ixazomib administration should be modified as noted as per dose modification recommendations in the protocol when thrombocytopenia occurs (see [Table 8.2](#)). Therapy can be reinitiated at a reduced level upon recovery of platelet counts. A rare risk is thrombotic thrombocytopenic purpura (TTP), a rare blood disorder where blood clots form in small blood vessels throughout the body characterized by thrombocytopenia, petechiae, fever, or possibly more serious signs and symptoms. TTP should be managed symptomatically according to standard medical practice.

9.9c Neutropenia

Blood counts should be monitored regularly as outlined in the protocol with additional testing obtained according to standard clinical practice. Neutropenia may be severe but has been manageable. Growth factor support is not required but may be considered according to standard clinical practice. Ixazomib administration should be modified as noted as per dose modification recommendations in the protocol when neutropenia occurs (see [Table 8.2](#)). Therapy can be reinitiated at a reduced level upon recovery of ANC.

9.9d Fluid Deficit

Dehydration should be avoided since ixazomib may cause vomiting, diarrhea, and dehydration. Acute renal failure has been reported in patients treated with ixazomib, commonly in the setting of the previously noted gastrointestinal toxicities and dehydration. Fluid deficit should be corrected before initiation of study drug and as needed during treatment to avoid dehydration.

9.9e Hypotension

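### The ixazomib restart sentence in Table 8.2 has no fever condition, so the row both directs omission and permits restart for a patient who is still febrile

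*Combined protocol and SAP*

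**What the plan says.** The blood and lymphatic row of Table 8.2 (Section 8.2) opens "Febrile neutropenia If platelet count" and lists three alternative reasons to omit ixazomib on Days 2-15: platelets below 30 × 10⁹/L, ANC below 1.0 × 10⁹/L, or ANC above 1.0 × 10⁹/L "up to LLN) with fever" above 38.5 °C. Blood counts are then followed weekly. The restart condition is an ANC of at least 1.0 "and/or platelet counts" of at least 30, after which "ixazomib may be reinitiated with 1 dose level reduction".

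For pomalidomide, Table 8.3 has the same ANC and fever trigger. If the neutropenia has improved to Grade 2 or better "prior to Day 21 and fever has resolved, restart pomalidomide at next lower dose level". The same cell adds that, where febrile neutropenia is the only reason for a reduction, "G-CSF may be used and the pomalidomide dose maintained".

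Sections 9.9b (thrombocytopenia) and 9.9c (neutropenia) refer to Table 8.2. Section 9.9b says: "Therapy can be reinitiated at a reduced level upon recovery of platelet counts". Section 9.9c says the equivalent for ANC. Neither mentions fever.

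Section 8.0 makes the modifications strict for the first two cycles and guidelines afterwards.

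**The concern.** A restart rule should undo the condition that caused the omission. Here one of the three conditions includes fever, and the restart test does not. For that limb the test is already satisfied when the dose is omitted, so it tells the clinician nothing about recovery.

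What is at stake is a dose of a drug that Section 9.9g calls immunosuppressive, given to a patient who is febrile with an ANC below normal. The wording matters most in cycles 1 and 2, where staff are told to follow the table strictly because individual tolerance is not yet known.

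**Working it through.** The documents state no figure to reproduce. The check is a logical comparison. Counts are × 10⁹/L, and values exactly on a threshold are set aside.

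**Step 1. Each omission limb against the restart test, with 'and/or' read as recovery of the affected count, the meaning that 9.9b and 9.9c support.**

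| Reason for omission | State at omission | Restart test already met? |
|---|---|---|
| Low platelets | Platelets < 30 | No; platelets must reach 30 |
| Low ANC | ANC < 1.0 | No; ANC must reach 1.0 |
| Fever limb | ANC > 1.0 up to LLN, fever > 38.5 °C, platelets ≥ 30 | Yes; ANC > 1.0 implies ANC ≥ 1.0, and platelets are ≥ 30 |

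The third line is the same if 'and/or' is read as 'and' or as 'or', since both counts are at or above threshold.

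**Step 2. How much of the rule is affected.** Take platelets (< 30, ≥ 30), ANC (< 1.0, 1.0 to LLN, > LLN) and fever (no, yes): 2 × 3 × 2 = 12 combinations. Omission is triggered in:
- platelets < 30: 3 × 2 = 6;
- platelets ≥ 30 and ANC < 1.0: 2;
- platelets ≥ 30, ANC 1.0 to LLN, fever: 1.

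The total is 6 + 2 + 1 = 9. With the affected count required to recover, restart is also permitted in 1 of these 9, the fever state. These are logical combinations, not patients.

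**Step 3. Does another section supply the missing condition?** Section 8.11 requires non-hematologic treatment-related events to have settled, but only before Day 1 of a new cycle. Sections 9.9b and 9.9c speak only of counts. Within Table 8.2, the other four omit-then-restart rows (neuropathy Grade 2 with pain or Grade 3, neuropathy Grade 4, rash, other non-hematologic Grade 3) all tie restart to resolution or recovery; the first, for example, reads "Omit ixazomib until AE resolves or returns to baseline". Table 8.3 asks for fever resolution on the same trigger. Because it also offers G-CSF with the pomalidomide dose kept, it supports the comparison but is not decisive.

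**Step 4. Which dose is at stake.** Ixazomib is given on Days 1, 8 and 15, and omitted doses are not made up. Within a cycle, a restart after a Day 8 omission can affect only Day 15. After a Day 15 omission, the next dose is Day 1 of the following cycle, where Section 8.11 applies.

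**Step 5. The secondary point.** Read literally, 'and/or' lets one adequate count suffice while the other is still low. Table 8.2 does not rule this out; 9.9b and 9.9c do so by implication.

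**The case against.** The strongest reply is that the omission trigger is not spent once used. Day 15 lies inside the Days 2-15 window, so a patient who is febrile that day with ANC between 1.0 and LLN meets the trigger again. Reading the instruction to omit together with the permission to restart, a careful clinician would treat the permission as operating only when no trigger is present. That stands. A reader might infer that the protocol orders re-dosing of febrile patients; it does not. The row conflicts with itself, and the restart side is only permissive.

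A reader might also infer from the literal 'and/or' that the plan means to allow restart while the affected count is still low. Sections 9.9b and 9.9c contradict that, so this part is loose drafting and should not be used to enlarge the finding.

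There are partial safeguards. In induction and consolidation the same trigger also invokes Table 8.3, so fever normally has to be considered for that patient. An attributable Grade 3 infection would fall under the row for other non-hematologic Grade 3 events, which requires recovery. But Table 8.3 governs pomalidomide, which is not given in maintenance, and the other row reaches only attributable Grade 3 events.

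These points limit the consequence without removing the error. A sentence that has to be disregarded to dose as the rest of the row directs should be corrected.

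**Conclusion.** Wrong as written, minor. With platelets at least 30, a patient omitted on the fever limb meets the ixazomib restart test while still febrile, and no other section adds a fever condition to a within-cycle restart. The conclusion follows from the wording alone and does not depend on how 'and/or' is read.

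Its size is 1 of 9 omission states on the reading that 9.9b and 9.9c support. In practice it concerns a possible Day 15 dose after a Day 8 omission. The documents give no frequency for this situation, so no number of patients can be attached. Nor can a firm limit on restarts per patient be derived from the dose ladder: for events attributed to both drugs, the note under Table 8.2 alternates reductions starting with pomalidomide, so such an event need not use up an ixazomib level.

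A reader might suspect an effect on the trial's result. There is none to show: the 18-month endpoint, the 21-patient decision rule and the analysis do not depend on this sentence.

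**What to change.** Reword the restart sentence in Table 8.2 as follows: If ANC is ≥ 1.0 × 10⁹/L and platelet count is ≥ 30 × 10⁹/L, and any fever that led to the omission has resolved, "ixazomib may be reinitiated with 1 dose level reduction".

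This keeps both thresholds, replaces 'and/or' with a requirement on both counts, and brings the fever condition into line with Table 8.3. In the one conflicting state the fever limb is the only trigger met, so restart is now refused and the overlap falls from 1 of 9 to 0 of 9. Tying the clause to the fever that caused the omission also covers a patient whose ANC later rises above LLN while that fever persists. A clause checking fever only when ANC is below LLN would miss that patient. An unrelated fever with ANC above LLN does not block restart. A new fever with ANC between 1.0 and LLN, arising after a count-based omission, is caught by applying the existing omission trigger on the dosing day.

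The cost is one sentence and an occasional withheld Day 15 dose. Sample size, endpoint, visit schedule and analysis are unchanged.
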